7.7 DATA AND SAFETY MONITORING PLAN

7.7.1 Principal Investigator/Research Team

The NCI Principal Investigator, NCI lead associate investigator and the NCI research nurse will meet weekly at each clinic and also conference calls will be held every 6 weeks with each participating sites to review all adverse events for each subject in this trial and to determine dose limiting toxicities and escalation rules.

Unexpected adverse events and/or serious adverse events will be reported to the NCI's Institutional Review Board (IRB) and sponsor/FDA as outlined above. If trends are noted and/or risks warrant it, accrual will be interrupted, dose levels expanded and/or the protocol and/or consent will be modified accordingly.

All data will be collected in a timely manner and reviewed by the principal investigator or a lead associate investigator. Adverse events will be reported as required above. Any safety concerns, new information that might affect either the ethical and or scientific conduct of the trial, or protocol deviations will be immediately reported to the IRB using iRIS.

The principal investigator will review adverse event and response data on each patient to ensure safety and data accuracy. The principal investigator will personally conduct or supervise the investigation and provide appropriate delegation of responsibilities to other members of the research staff.

7.7.2 Sponsor Monitoring Plan

As a sponsor for clinical trials, FDA regulations require the CCR to maintain a monitoring program. The CCR's program allows for confirmation of: study data, specifically data that could affect the interpretation of primary study endpoints; adherence to the protocol, regulations, and SOPs; and human subjects protection. This is done through independent verification of study data with source documentation focusing on:

- Informed consent process
- Eligibility confirmation

- Drug administration and accountability
- Adverse events monitoring
- Response assessment.

The monitoring program also extends to multi-site research when the CCR is the coordinating center.

This trial will be monitored by personnel employed by a CCR contractor. Monitors are qualified by training and experience to monitor the progress of clinical trials. Personnel monitoring this study will not be affiliated in any way with the trial conduct.

7.7.3 Safety Monitoring Committee (SMC)

This protocol will require oversight from the Safety Monitoring Committee (SMC). Initial review will occur as soon as possible after the annual NCI-IRB continuing review date. Subsequently, each protocol will be reviewed as close to annually as the quarterly meeting schedule permits or more frequently as may be required by the SMC. For initial and subsequent reviews, protocols will not be reviewed if there is no accrual within the review period. Written outcome letters will be generated in response to the monitoring activities and submitted to the Principal investigator and Clinical Director or Deputy Clinical Director, CCR, NCI.

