2.3.2 Treatment Assignment and Randomization Procedures

Cohorts

Number	Name	Description
1	Prostate Cancer	Male patients diagnosed with prostate cancer (non-metastatic), with demonstrated biochemical progression, a PSA doubling time of 5-15 months, and with a rising PSA.

Arms

Letter	Name	Description
A	PROSTVAC treatment	PROSTVAC treatment for 6 months with an additional optional year of maintenance for eligible patients
B	Delayed PROSTVAC treatment	Surveillance for 6 month followed by PROSTVAC treatment for 6 months with an additional year of maintenance for eligible patients

Randomization and Arm Assignment

Subjects in Cohort 1 will be randomized on a 1:1 basis to **Arm A** or to **Arm B**. The computerized randomization will be performed by the NCI Central Registration Office. CRO staff will send a secured e-mail with the Verification of Registration of the patient and treatment arm patient is randomized to. This process will be completed within 15–30 minutes of sending the eligibility checklist. CRO will keep track of all randomization data in Clinical Data Registry (CDR) of CRO.

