11.2 RECOMBINANT VACCINIA-PSA(L155)/TRICOM™

Other Names: PROSTVAC-V/TRICOM™; PROSTVAC-V

Classification: Recombinant vaccinia virus vector vaccine of the genus *Orthopoxvirus*.

Product Description: Recombinant Vaccinia-PSA(L155)/TRICOM™ is a recombinant vaccinia virus vector vaccine containing the genes for human PSA and three co-stimulatory molecules (designated TRICOM™): B7.1, ICAM-1 (intercellular adhesion molecule-1), and LFA-3 (leukocyte function-associated antigen-3). The PSA gene coding sequence is modified to code for a single amino acid substitution [isoleucine to leucine at amino acid position 155 of the PSA antigen (designated L155)], which is designed to enhance immunogenicity. This modification occurs in a 10-mer, HLA-A2-restricted, immunodominant epitope of the antigen [designated PSA-3 (amino acids 154-163)]. An attenuated, live, derivative of the Wyeth (New York City Board of Health) strain of vaccinia virus is used as the parental virus for the recombinant vaccine. A plasmid vector containing the modified PSA gene and the genes for the three co-stimulatory molecules is used for *in vivo* recombination between the plasmid vector and parental vaccinia virus genome. The recombinant vaccine is manufactured by infection of primary chicken embryo dermal (CED) cells with the recombinant vaccinia virus. Vaccinia virus can infect mammalian cells and express the inserted transgenes, and is a potent immune stimulator, eliciting both a strong humoral and cellular immune response. Vaccinia virus is replication competent in mammalian cells, making systemic infections possible.

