15 APPENDIX C : FOLLOW-UP EVALUATIONS

STUDY CALENDAR

Surveillance ARM – PROSTVAC: surveillance for 6 months followed by vaccinia-PROSTVAC, 2×10^8 infectious units subcutaneously in week 1 and fowlpox-vaccine 1×10^9 infectious units subcutaneously given in week 3, week 5 and then monthly for a total of 6 months of treatment. After this 6-month treatment period is complete, patients will then have the option of fowlpox-vaccine 1×10^9 q 3 months for 1 year while in follow-up.

	Screening/ Baseline ¹¹	Surveillance for 6 months							1 cycle = 28 days; C=Cycle; D=Day											
		M -6	M -5	M-4	M-3	M-2	M-1	C1 D1	C1 D15	C2 D1	C3 D1	C4 D1	C5 D1	C6 D1	C7 D1	C8 D1	C9+ D1 ^{6,7}	End of study		
Informed Consent / Registration	X																			
Randomization	X																			
TREATMENT																				
rV-PROSTVAC									X											
rF-PROSTVAC										X	X	X	X	X	X		X ⁹			
EVALUATION																				
History and PE, Height and Weight	X		X		X		X		X	X	X	X	X	X	X	X	X ¹	X		
ECOG Performance Score	X																			
Pathologic confirmation of dx	X ²																			
Laboratory Testing																				
CBC with differential	X								X	X	X	X	X	X	X	X	X ¹	X		
Serum chemistries (Na ⁺ , K ⁺ , Cl ⁻ , CO ₂ , glucose, BUN, creatinine, albumin, calcium, alkaline phosphatase, ALT, AST, total bilirubin, LDH,)	X								X	X	X	X	X	X	X	X	X ¹	X		
CK, uric acid, total protein, magnesium, phosphorus,	X																			

	Screening/ Baseline ¹¹	Surveillance for 6 months							1 cycle = 28 days; C=Cycle; D=Day											
		M -6	M -5	M-4	M-3	M-2	M-1	C1 D1	C1 D15	C2 D1	C3 D1	C4 D1	C5 D1	C6 D1	C7 D1	C8 D1	C9+ D1 ^{6,7}	End of study		
Urinalysis	X																			
Serum PSA and Testosterone	X	X	X	X	X	X	X	X	X	X	X	X	X	X	X	X ¹	X			
Hep B/HepC, HIV	X ³																			
Lymphocyte Phenotyping (CD4/CD8) ¹²	X							X	X	X	X	X	X	X	X	X ¹	X			
PAP (prostatic acid phosphatase)	X							X	X	X	X	X	X	X	X	X	X			
ECG	X ⁵																			
Tc 99 scintigraphy	X ⁴							X								X ⁶				
CT-C/A/P, or MRI	X ⁴							X								X ⁶				
Research Bloods	X							X		X				X		X ⁷	X ⁸			
FACT- P survey ¹⁰		X ¹⁰						X ¹⁰			X ¹⁰			X ¹⁰			X ¹⁰			
MSK Anxiety Survey ¹⁰		X ¹⁰						X ¹⁰			X ¹⁰			X ¹⁰			X ¹⁰			
Adverse Events	X		X		X		X	X									→			
Concomitant Medications	X							X									→			

Footnotes:

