² Pathologic confirmation will be obtained anytime prior to enrollment

³ HepB/HepC/HIV status will be obtained within 8 weeks prior to enrollment

⁴ Screening Tc99 scintigraphy and CT-CAP or MRI will be obtained within 8 weeks prior to enrollment

⁵ Baseline ECG will be obtained within 8 weeks prior to enrollment

⁶ Restaging will be done every 6 months (+/- 14 days) or earlier if clinically indicated. If, however, in the opinion of the investigator re-staging scans are not required (in patients with a PSA DT > 6 month over the previous 6 months, document in chart to assure compliance) then re-staging scans can be deferred. However, once PSA DT is less than 6 months, scans must be performed.) Re-staging scans may exclude CT Chest.

⁷ Patients will continue to be followed after Cycle 9 until progression or ADT is clinically indicated. All visits will include evaluations listed for cycle 9 except research blood. Research blood will not be drawn after Cycle 9..

⁸optional

⁹ Patients will have the option to initiate 1 year of vaccine maintenance within 3 months of cycle 6 vaccine, administered every 12 weeks. This year will include follow-up every 6 weeks during this period for PSA checks on non-vaccine visits. (Patients seen every 6 weeks during 1 year maintenance period). Patients will be required to have a PSADT greater than 5 months, as measured over the prior 6 months in order to start and continue vaccine during the 1 year maintenance period.

¹⁰Surveys are optional at all time points and can be done every 3 months for the first 9 months and every 3-4 months thereafter while patients are on-study. (If surveys are not done, reason will be documented.)

¹¹ Refer to sections [2.2](#) for screening evaluation and [2.4](#) for baseline evaluation

¹² Not performed at DFCI site.

-All patient visits can be delayed by 2 weeks for logistical issues except for week 3 and 5 where the window is 3 days.

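### Section 7.7.3 cancels Safety Monitoring Committee review in any period without accrual, although Arm B starts vaccinia 6 months after randomisation and dosing can run to about month 22

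*Combined protocol and SAP*

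**What the plan says.** Section 7.7.3 places the protocol under SMC oversight. After the initial review, each protocol is to be "reviewed as close to annually as the quarterly meeting schedule permits". The committee may also ask for reviews at shorter intervals. One condition governs first and later reviews alike: "protocols will not be reviewed if there is no accrual within the review period". The section says nothing about patients who are still receiving vaccine when accrual is closed.

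Section 2.3.2 describes Arm B as "Surveillance for 6 month followed by PROSTVAC treatment for 6 months with an additional year of maintenance for eligible patients". The Arm B calendar in Appendix C confirms that the first product given is vaccinia: "surveillance for 6 months followed by vaccinia-PROSTVAC". Footnote 9 of that calendar adds: "Patients will have the option to initiate 1 year of vaccine maintenance within 3 months of cycle 6 vaccine, administered every 12 weeks". Section 3.1 gives the maintenance year as 4 doses. Section 11.2 says of the first product: "Vaccinia virus is replication competent in mammalian cells, making systemic infections possible".

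**The concern.** A rule that stops committee review when accrual stops is reasonable where treatment begins at enrolment and is short. In this trial accrual is a poor guide to exposure. On the day accrual closes, Arm B men randomised in the previous 6 months have not yet had vaccinia, the replication-competent product. Both arms may also have maintenance doses still to come.

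Followed as written, the rule ends the SMC's scheduled reviews while men may still be vaccinated. The cumulative safety data from delayed vaccination in Arm B and from maintenance would be complete only after the committee had stopped looking. At stake is the quality of safety oversight late in the trial. The primary comparison is not affected.

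**Working it through.** The plan states no figure for dosing after the last randomisation, so there is nothing to reproduce. The schedule can be added up.

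**Inputs**
- Surveillance before vaccine in Arm B: 6 months (2.3.2, Appendix C).
- Cycle length: 28 days, with the last induction dose at cycle 6 day 1 (Appendix C).
- Maintenance: starts within 3 months of the cycle 6 vaccine, then every 12 weeks (Appendix C, footnote 9); 4 doses (3.1).
- SMC review: about every 12 months (7.7.3).
- Accrual: 4 years, 36 evaluable men in Arm B (Section 8).
- Conversion: 30.44 days per month.

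**Step 1. Last-randomised Arm B man, months from randomisation**
- First vaccinia dose: 6.0.
- Last induction dose: 6 + (5 × 28)/30.44 = 6 + 4.6 = 10.6.
- Last maintenance dose, latest permitted start: 10.6 + 3.0 + (3 × 84)/30.44 = 10.6 + 3.0 + 8.3 = 21.9.

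The last figure becomes 20.7 if maintenance starts 8 weeks after cycle 6, 22.3 if cycle 6 is delayed by 14 days, and 24 on nominal calendar months (6 + 6 + 12).

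**Step 2. Dosing after the last SMC review**

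The period that contains the last randomisation still has accrual, so it is reviewed. Let R be the time from the last randomisation to that review, between 0 and 12 months.
- Full maintenance: 21.9 − R, which is 21.9 months at R = 0 and 9.9 months at R = 12. If the review slips by a quarter to R = 15, it is 6.9 months.
- No maintenance: 10.6 − R, not below zero. This is 10.6 months at R = 0 and zero once R reaches 10.6.
- The last-randomised man's vaccinia dose falls after the last review whenever R is below 6.

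**Step 3. Vaccinia doses after the last SMC review**

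Assume even accrual: 36/48 = 0.75 Arm B men per month.
- Vaccinia doses given after accrual closes: 0.75 × 6 = 4.5 of 36.
- All 4.5 follow the last review if R = 0; none do if R is 6 or more.
- Assume also that R is uniform on 0 to 12 months. A dose given t months after closure then follows the last review with probability t/12. The expected number is 0.75 × ∫₀⁶ (t/12) dt = 0.75 × 36/24 = 1.1 of 36, about 3%.

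**Step 4. Other safety review, and whether it depends on accrual**
- NCI-IRB continuing review receives a table of related grade 3 and 4 events, unexpected related grade 2 events, all grade 5 events and all serious events (7.2.2). It is not tied to accrual.
- The Institutional Biosafety Committee (IBC) receives annual reports until the trial is completed, with adverse experiences by body system, serious events and deaths (7.6.2). These are not tied to accrual.
- Expedited serious-event reporting (7.4, 7.6.1) and the study halting rule (8.1.1) are not tied to accrual.
- Research-team meetings and site calls (7.7.1) and sponsor monitoring (7.7.2) are not tied to accrual.
- SMC review (7.7.3) is the only one conditional on accrual.

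**The case against.** The strongest objection is that much else continues. A reader might infer from 7.7.3 that all committee-level safety oversight ends, or that the SMC is the only outside body seeing accumulating data. The documents do not support that. The IRB and the IBC both receive cumulative safety data whether or not accrual is open, and serious events still reach the sponsor promptly. An annual committee is not the main detector of acute vaccinia harm. This objection stands and limits the point to SMC review. It does not justify the rule, because 7.7.3 requires the SMC in addition to those channels. Nor do the grade 4 and 5 rules name the SMC: 3.1.1 has the investigator halt accrual and consult the IRB, which achieves little once accrual has closed, and 8.1.1 halts the study but names no reviewing body.

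Second, a reader might take 4.5 vaccinia doses, or 22 months, as the amount that goes unreviewed. Each is an upper limit. The 4.5 counts doses after accrual closes, some of which the final review may cover. The 22 months needs a last-randomised Arm B man who takes every maintenance dose, keeps a PSA doubling time above 5 months and is randomised just before a review.

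Third, late doses are not a new exposure. Arm A receives the same products from the start, most Arm B vaccinia doses precede closure (31.5 of 36 under even accrual), and Section 1.2.3 reports no safety concern so far. That lowers the urgency.

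Fourth, the wording reads like the committee's standing practice, and its charter is not among the documents. The SMC may ask for more frequent review, but the text does not say that this overrides the no-accrual condition.

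**Conclusion.** The point holds in limited form. Followed exactly, 7.7.3 ends scheduled review by the trial's designated safety committee while men may still be vaccinated, for a reason unrelated to their risk. The length of dosing after the last SMC review depends on where the last randomisation falls in the annual cycle:
- without maintenance, 0 to about 10.6 months;
- with full maintenance, about 10 to 22 months.

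Between 0 and 4.5 of 36 Arm B vaccinia doses would follow the last review, with about 1.1 expected. The range rests on even accrual over 4 years, and the expected value also on uniform review timing. The upper durations assume 4 maintenance doses at the latest permitted start. Nothing here shows that harm has occurred or that other oversight stops. It is a cheap improvement to the monitoring plan.

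**What to change.** In 7.7.3, replace the no-accrual condition with: *The protocol will be reviewed in every review period in which any patient is accrued, receives vaccine, or is within the post-vaccine adverse-event follow-up period.* Section 6.1 already defines that follow-up as at least 30 days after removal from study treatment, or until off-study if sooner.

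The cost is small. With full maintenance, the last Arm B dose plus 30 days falls at about 21.9 + 1.0 = 22.9 months after the last randomisation. Annual review then means one or two more reviews than the present rule gives. They would use the existing quarterly SMC meetings and data already collected, with no new visits and no change to any dose or schedule. If the current sentence is the SMC's standing practice, the change should be agreed with the committee first.

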8 STATISTICAL CONSIDERATIONS

The primary endpoint of this trial is to determine if prostvac can slow the growth rate of prostate cancer relative to a group of patients on surveillance. With 36 evaluable patients with a growth rate value from 0 to 6 months on the Prostvac arm and 36 evaluable patients on the surveillance arm (72 total patients) there would be adequate patients to have 80% power to test for a difference between the two arms of a change in growth rate from baseline equal to 2/3 SD of the change (0.67 SD effect size) using a 0.05 significance level two-tailed two group t-test. In practice, if the distributions of the growth rate constants are not normally distributed ($p < 0.05$ by a Shapiro-Wilks test), then a Wilcoxon rank sum test may be used instead of a two-sample t-test. In order to allow for a small number of inevaluable subjects as well as to accommodate screen failures, the accrual ceiling will be set at 110. (It is estimated that it will take 4 years to complete accrual to this trial.)

Secondary Endpoints

In addition, using the surveillance arm, two related endpoints will be explored, both the actual magnitude of the change in the growth rate parameter as well as the fraction who exhibit a substantial, 50% decline in the growth rate as a result of treatment. For the 36 patients who will be enrolled on the surveillance arm, the growth rate determined at 12 months (after 6 months of vaccine) will be subtracted from that obtained at 6 months (after surveillance) to determine the actual change in the growth rate for receiving vaccine after 6 months of surveillance. With 36 patients, there is 83% power to detect a difference in the values at the two time points equal to 1/2 of the SD of the change (.50 effect size) assuming that a two tailed 0.05 alpha level paired t-test is used.

As an additional secondary exploration, using all 36 patients on the surveillance arm, the fraction that experiences a 50% decline relative to the time of starting vaccine will be determined. Using an exact binomial test, 36 patients will have 79% power to test whether the fraction exceeds a null fraction of 30% and is consistent with 50% who have 50% declines, with a one-tailed 0.05 alpha level test. In practice, the fraction with a 50% decline will have a 95% confidence interval created about the result in order to describe what values it would be consistent with. Exploratory analyses will also be performed to compare the growth rate changes at additional time points, such as 10 and 12 months.

Immune response generated by prostvac will also be evaluated and will be compared to the fraction of patients on the two arms who have a substantial T cell response as measured by exposure to overlapping PSA peptides. The patients will be considered to have had a T cell response if there is at least a 2 fold increase in immune response compared to baseline. This response is expected to be minimal during the first 6 months on the surveillance arm and more pronounced on the arm receiving Prostvac initially. With 36 patients per arm, there is 80% power to detect a difference between 10% with immune response on the surveillance arm and 40% on the Prostvac arm, with a two-sided 0.05 significance level using Fisher's exact test. Should only 29 patients per arm have evaluable immune response data, there would be 81% power to detect a difference between 10% and 45% with immune responses.

Other secondary endpoints include performing immune response evaluation including CD4 cells, CD8 cells, PSA-specific T-cells, natural killer cells, Regulatory T-cells, Regulatory T-cell function, cytokines, and naïve thymic emigrants; and associating immunologic outcomes with PSA responses/changes in growth rates. (This could be done every 6 months). Each of these endpoints will be analyzed using appropriate nonparametric methods when applicable and the results from these analyses will be presented without formal adjustment for multiple comparisons, but in the context of the number of such evaluations undertaken.

Beginning with amendment G, patients enrolled onto either the immediate vaccine arm or the surveillance followed by vaccine arm will be asked to complete a prostate cancer specific QOL survey with 18 questions (MAX-PC) as well as the FACT-P survey at the following time points:

Immediate vaccine Arm

Baseline; 3 months; 6 months; 9 months; approximately q3-4 months in follow-up

Surveillance Arm

-6 months; -3 months; Baseline/start of vaccine; 3 months; 6 months; 9 months; approximately q3-4 months in follow-up.

The surveys will each be scored using the appropriate conventional scoring method to arrive at a total score for each instrument at each of the indicated time points. The changes in total score from baseline to each of the time points will be determined (for the surveillance arm, changes from -6 months and -3 months will also be determined), and each of the changes will be tested for statistical significance from zero change using a paired test (either paired t-test or Wilcoxon signed rank test depending on whether all the changes are normally distributed or not). The tests will be performed with exploratory intent and the results of the tests will be reported without

formal adjustment for multiple comparisons. In addition to evaluating the actual changes, the correlation between the two measures (MAX-PC and FACT-P) at each time point will be determined using Spearman correlation and will be reported as an exploratory result along with an interpretation of the magnitude of the correlation. Finally, the correlation of the changes in the scores with the change in growth rate at the corresponding time points will be determined and reported as an exploratory finding, along with interpretation of the magnitude of the correlation.

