1.1.3 Exploratory Endpoints

Beginning with amendment G, patients enrolled onto either the immediate vaccine arm or the surveillance followed by vaccine arm will be asked to complete a prostate cancer specific QOL survey with 18 questions (MAX-PC) as well as the FACT-P survey. Associations will be made between survey responses and changes in PSA kinetics.

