3.4 QUESTIONNAIRES

3.4.1 Evaluating Quality of Life in this Population

Little has been formally evaluated about the impact of PSA kinetics on patients with BCR. Beginning with amendment G, patients enrolled onto either the immediate vaccine arm or the surveillance followed by vaccine arm will be asked to complete a prostate cancer specific QOL survey with 18 questions (MAX-PC) as well as the FACT-P survey at the following time points:

Immediate vaccine Arm

Baseline; 3 months; 6 months; 9 months; approximately q3-4 months in follow-up

Surveillance Arm

-6 months; -3 months; Baseline/start of vaccine; 3 months; 6 months; 9 months; approximately q3-4 months in follow-up

Each survey will take approximately 5 minutes to complete and they will be administered in english. The surveys being used have been published and vetted as appropriate QOL tools²¹⁻²³. This analysis will be done in an exploratory fashion as part of a collaboration with [name] who is an expert in prostate cancer QOL studies.

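### Quality-of-life change is tested only against zero; an exploratory between-arm estimate over the first six months would separate a vaccine difference from a shared time trend at little cost.

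*Combined protocol and SAP*

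**What the plan says.** Section 8 (Statistical Considerations) plans three analyses of MAX-PC and FACT-P.

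- **Change over time.** Total-score changes from baseline are formed, and "each of the changes will be tested for statistical significance from zero change using a paired test" (paired t or Wilcoxon signed rank, depending on normality). In addition, "for the surveillance arm, changes from -6 months and -3 months will also be determined".
- **Agreement.** Spearman correlation between the two instruments at each time point.
- **Link to PSA.** Correlation of score changes with change in growth rate.

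On status, Section 8 states: "The tests will be performed with exploratory intent". There is no multiplicity adjustment. On purpose, Section 1.1.3 states: "Associations will be made between survey responses and changes in PSA kinetics".

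The immediate vaccine arm (Arm A) is surveyed at "Baseline; 3 months; 6 months; 9 months; approximately q3-4 months in follow-up". The list for the surveillance arm (Arm B), whose first entry carries a minus sign, runs "6 months; -3 months; Baseline/start of vaccine; 3 months; 6 months; 9 months", with follow-up every 3-4 months after that. In Arm B the label baseline therefore means the start of vaccine, six months after the surveillance period began.

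On allocation, Section 2.3.2 states: "Subjects in Cohort 1 will be randomized on a 1:1 basis to" Arm A or Arm B. Sections 1.1.3, 3.4.1 and 8 specify no comparison of quality-of-life change between the arms. Section 8 does specify between-arm tests for the primary endpoint and for T-cell response.

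**The concern.** A test of change against zero asks whether scores moved. It cannot say whether they moved because of the vaccine or because time passed on trial. Drift is plausible here: MAX-PC asks directly about anxiety over PSA tests (Appendix H), and both arms have PSA measured at about monthly visits (Appendix C).

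The design can answer the sharper question. During Arm A's six months of vaccine, Arm B is unvaccinated, concurrent, randomised and surveyed with the same instruments. A trend shared by both arms cancels in a comparison between them. Without that comparison, a significant change after vaccine start has no planned control. No primary or secondary conclusion depends on this; what is at stake is how much the quality-of-life data can support.

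**Working it through.** **Inputs from the documents.** Section 8 powers the primary comparison on "36 evaluable patients with a growth rate value from 0 to 6 months on the Prostvac arm" and the same number on surveillance, with a two-sided 0.05 two-group t-test and an effect of 2/3 SD of the change (given as 0.67). It also powers a paired t-test at 0.50 SD with 36 patients.

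**Assumptions.** The documents give no quality-of-life means or SDs, no count of survey completers, and no significance level for these particular tests. I take drift in SD units of the change, completers per arm from 12 to 36 (36 being the evaluable target), two-sided 0.05, and normally distributed changes.

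**Step 1: reproduce the plan's own figures.**

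- Two-sample t, noncentrality = d × √(n/2). With n = 36 and d = 2/3: 0.667 × √18 = 2.83, 70 df, power 79.7%. With d = 0.67: 80.1%. The plan states 80%.
- Paired t, noncentrality = d × √n. With n = 36 and d = 0.50: 0.50 × 6 = 3.0, 35 df, power 83.1%. The plan states 83%.

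The same formulas are used below.

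**Step 2: planned test, with shared drift and no vaccine effect.** For drift 0.3 SD, noncentrality = 0.3 × √n, against the two-sided critical t on n − 1 df.

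| Completers in the arm | 0.3 × √n | Critical t | Probability significant |
|---|---|---|---|
| 12 | 1.04 | 2.20 | 15.8% |
| 18 | 1.27 | 2.11 | 22.5% |
| 24 | 1.47 | 2.07 | 29.1% |
| 30 | 1.64 | 2.05 | 35.6% |
| 36 | 1.80 | 2.03 | 41.7% |

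With 36 completers the range over other drift sizes is 9.0% (0.1 SD), 21.5% (0.2 SD) and 83.1% (0.5 SD).

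**Step 3: between-arm test under the same conditions.** If both arms drift by τ and the vaccine effect is zero, the expected difference in change is τ − τ = 0, whatever τ is. Simulation with 36 per arm and 20,000 runs gave rejection rates of 4.7% to 5.3% for drifts from 0 to 0.5 SD.

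**Step 4: can the two arms' p-values be read side by side instead?** With equal drift and independent arms, exactly one arm is significant with probability 2p(1 − p). At 0.3 SD and 36 per arm, 2 × 0.417 × 0.583 = 48.6%. Nearly half the time, two arms with identical drift would appear to differ.

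**Step 5: precision of the comparison.** The difference in change detectable with 80% power (two-sample t) is 0.67 SD at 36 per arm, 0.83 at 24, 0.96 at 18 and 1.20 at 12. Baseline adjustment may improve on this, but the gain depends on a correlation that the documents do not give.

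**The case against.** The strongest reply is that the plan is being asked a question it did not pose. Section 1.1.3 sets the purpose as association with PSA kinetics, Section 3.4.1 gives the same motive, and the correlation of score change with growth-rate change serves it. No objective names a vaccine effect on quality of life. That stands, and it fixes the weight of the point.

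Three stronger readings are tempting, and the documents support none of them.

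- **That the plan attributes drift to the vaccine.** It does not. Section 8 tests whether scores changed and makes no statement about cause.
- **That the percentages in Step 2 are false-positive rates.** They are power to detect a real change. If scores drift by 0.3 SD, rejecting zero change is correct. An error arises only if a reader takes the result as evidence about the vaccine.
- **That the control data are discarded.** Surveillance-period changes in Arm B are determined and tested. Only the formal contrast is missing, although Step 4 shows that separate p-values do not replace it.

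The proposed contrast also has limits. No placebo or blinding is described for the surveillance period, so expectation effects would enter any comparison of self-reported anxiety. Surveys are optional at every time point (Appendix C footnotes) and began with amendment G, so completers may be few and selected. Survey timing needs confirming: in the copy available, the Appendix C calendars appear to mark Arm A's later survey at Cycle 6 Day 1 (5 × 28 + 1 = day 141) and show no mark at month -3 in Arm B. Column alignment is uncertain in that copy, so this is a caution and not a finding.

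**Conclusion.** The point holds as a low-cost improvement. Every planned test of quality-of-life change is against zero, no planned analysis contrasts the randomised arms, and a change after vaccine start therefore cannot be separated from a time trend. That these tests run within each arm is implied by the arm-specific schedules and is not stated in words.

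Under an assumed shared drift of 0.3 SD, the paired test would be significant in a given arm between about 16% (12 completers) and 42% (36 completers) of the time with no vaccine effect, against about 5% for a between-arm test. Both the drift and the completer numbers are assumptions. The exploratory label deals with multiplicity; it does not deal with confounding by time. No stated conclusion of the trial is wrong because of this.

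**What to change.** Add to Section 8, for each instrument, an exploratory ANCOVA of the six-month total score on randomised arm, adjusted for the score at randomisation:

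- **Six-month score:** Arm A month 6; Arm B start of vaccine, completed before the first Arm B vaccination.
- **Score at randomisation:** Arm A baseline; Arm B month -6. The text should say explicitly that Arm B's start-of-vaccine score is not the baseline for this comparison.
- **Report:** the adjusted difference with a 95% CI, and the number of completers in each arm at each time point.
- **Stop at six months.** After that Arm B is vaccinated too, and there is no unvaccinated comparator.

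Keep the paired tests as descriptive and keep the planned correlations with growth rate. Reconcile the survey times in Sections 3.4.1 and 8 with the Appendix C calendars so that the two arms line up.

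The cost is a short paragraph and a few lines of analysis, with no new data, visits or patients. The text should state the limits: open-label surveillance without placebo, optional surveys from amendment G onward, and low precision if completers are few.
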